### List A: Inhibitors/substrates – prohibited 7 days before dosing and during study.

- azole antifungals (ketoconazole, itraconazole, miconazole, voriconazole)
- Non-dihydropyridine calcium channel blockers: verapamil, diltiazem
- Macrolide antibiotics: clarithromycin, erythromycin, telithromycin
- HIV protease inhibitors (indinavir, saguinavir, ritonavir, atazanavir, nelfinavir)
- delavirdine
- grapefruit juice

### List B: Inducers/substrates – prohibited 12 days before dosing and during study.

- rifampin
- Anti-convulsants: phenytoin, carbamazepine
- rifabutin
- St. John's wort
- efavirenz, nevirapine
- Barbituates: phenobarbital
- tipranavir
- 5.2.12 Patients with pre-existing hypothyroidism prior to enrolment are ineligible unless they are euthyroid on medication.
- 5.2.13 Because the effects of sunitinib on the developing human fetus and the newborn child at the recommended therapeutic dose are unknown, and because antiangiogenic agents are known to be teratogenic the following are exclusions for enrolment on the study:
- Pregnant or lactating women. (N.B.: All women of childbearing potential must have a negative urine •-HCG pregnancy test within 7 days prior to registration).
- Women of childbearing potential who do not agree to use adequate contraception (hormonal or barrier method of birth control; abstinence) prior to study entry and for the duration of study participation. (Should a woman become

pregnant or suspect she is pregnant while participating in this study, she should inform her treating physician immediately).

- 5.2.14 Known HIV-positive patients on combination antiretroviral therapy are ineligible because of the potential for pharmacokinetic interactions with sunitinib. In addition, these patients are at increased risk of lethal infections when treated with marrow-suppressive therapy. Appropriate studies will be undertaken in patients receiving combination antiretroviral therapy when indicated.
- 5.2.15 Greater than +1 proteinuria on urinary dipstick if also >1g urinary protein/24hrs

## 6.0 PRE-TREATMENT EVALUATION (all within 7 days of registration)

History	Physical Exam	Endocrine Testing		
Demographics	Height/weight	24-hour urinary metanephrines		
Diagnosis of malignancy	Vital signs	24-hour urinary catecholamines		
Prior therapy	ECOG performance status	serum chromogranin A		
Concurrent illness	Documentation of all measurable and non-measurable disease	TSH, T4		
Concomitant medications	Clinical tumour measurements (if applicable) within 7 days prior to registration			
NYHA functional status				
Baseline symptoms 				
Hematology	Biochemistry	Radiology (within 28 days)		
CBC + Differential	BUN	Chest Xray or chest CT scan		
PT/INR/PTT (if on coumadin or LMW heparin)	Serum creatinine or calculated creatinine clearance  (if serum creatinine > ULN)	Abdominal and pelvic CT scan		
	Sodium, potassium, chloride	Clinical tumour measurements		
Other	Bicarbonate			
urinalysis (dipstick for proteinuria) +/- 24 hr urine protein collect if >1+ on dipstick	Bilirubin			
Urine pregnancy test (pre- menopausal women of childbearing potential only)	Alkaline phosphatase			
EKG to determine QTc 	AST and ALT			
LVEF assessed by MUGA (for patients with class II NYHA, prior anthracyclines or central thoracic radiation, and at investigator's discretion in patients without cardiac risk factors) 	LDH			
Primary archival tissue block	Total protein			
	Calcium			
	Phosphate			
	Albumin			
	Fasting glucose			
	Amylase, lipase			
	CPK			
~				

Creatinine clearance to be measured directly by 24 hour urine sampling or as calculated by Cockcroft Formula: GFR = 1.04 x (140-age) x weight in kg NB: this version of the formula incorporates a 15% reduction for women

<sup>2 Adverse events will be recorded and graded using NCI Common Terminology Criteria for Adverse Events Version 3.0 (CTCAE)

<sup>3 EKG and LVEF assessed by MUGA within 21 days prior to registration

#### 7.0 REGISTRATION PROCEDURES

#### 7.1 General Guidelines

Following registration, patients should begin protocol treatment within 3 calendar days. Issues that would cause treatment delays should be discussed with the Principal Investigator. If a patient does not receive protocol therapy following registration, the patient's registration on the study may be cancelled. The Drug Development Program (DDP) Central Office Study Coordinator should be notified of cancellations as soon as possible.

### 7.2 Registration Process

Prior to registering a patient, each institution must have submitted all necessary regulatory documentation to the DDP Central Office Study Coordinator. Case report form (CRF) information will only be sent once this has been received.

No patient can receive protocol treatment until registration with the DDP Central Office has taken place. All eligibility criteria must be met at the time of registration. There will be no exceptions. Any questions should be addressed with the Principal Investigator (cc the central office study coordinator).

To register a patient, the following documents are to be completed by the research nurse or data manager and faxed to the DDP Study Coordinator:

- Signed patient consent form
- Eligibility Checklist signed by the investigator

To complete the registration process, the DDP Study Coordinator will review the checklist and once eligibility has been confirmed:

- Assign a patient study number
- Register the patient on the study
- Fax or e-mail the confirmation worksheet with the patient study number to the participating site

To ensure immediate attention is given to the faxed checklist, each site is advised to also call the DDP Study Coordinator. Patient registration will be accepted between the hours of 9am to 5pm Monday to Friday, excluding Canadian statutory holidays when the DDP Central Office will be closed.

### 7.3 Initial Drug Ordering and Resupply

Each participating institution will order sunitinib from the University Health Network – Princess Margaret Cancer Centre Pharmacy. Investigational agents may be ordered by a participating site only after the initial REB approval for the site has been received and the site has been activated by the DDP Central Office.

The participating site is responsible for requesting drug resupply by contacting the University Health Network – Princess Margaret Cancer Centre Pharmacy. A minimum of 7 business days is required to process the request for resupply.

#### 8.0 TREATMENT PLAN

### 8.1 Chemotherapy Treatment Plan

### 7.1.1 Drug Administration

Agent Dose Route Schedule sunitinib 50mg PO Daily once for 4 out of 6 weeks (1 cycle = 6 weeks) (4 weeks treatment plus 2 weeks observation). Sunitinib can be administered without regard to meals. Patients should be instructed to take their medication at approximately the same time every day. Doses should be recorded as appropriate on the CRF and patient diary.

#### 8.1.2 Premedications

No routine premedications are advised but see section below for guidance of symptom management if required.

### 8.1.3 Supportive Care

The following are some general recommendations for management of sunitinib effects:

### Nausea/Vomiting

Patients with treatment-related nausea should be treated initially with prochlorperazine – 10 mg every 8 hours orally as needed. If this is inadequate, a benzodiazepine such as lorazepam may be added until acute nausea is controlled or toxicity is limiting. Should this prove inadequate acutely, a steroid may be added in standard doses. Although QTc prolongation has not been seen in clinical trials, preclinical studies suggest sunitinib has the potential to prolong QTc. Therefore, since 5-HT3 antagonists have some effects on ECG intervals, 5-HT3 antagonists should be used with caution and patients should be monitored appropriately for any ECG changes or QTc prolongation. After acute nausea has resolved, consideration should be given to initiation of prophylactic antiemetic therapy. If nausea recurs despite reasonable medical intervention (as outlined above), dose reduction will be needed as described in Section 8.3.

#### Diarrhoea

Diarrhoea should be managed with loperamide: 4 mg at first onset, then 2 mg every 2-4 hours until diarrhoea is controlled (maximum = 16 mg loperamide per day).

### Hand-foot Syndrome

Hand-foot syndrome may be treated with topical emollients, topical or systemic steroids, and/or antihistamine agents as needed. Vitamin B6 (pyridoxine; 50-150 mg orally each day) may also be used.

### Complications of Myelosuppression:

Neutropenic fever or infection with neutropenia should be evaluated promptly and treated with antibiotic therapy with/without therapeutic colony-stimulating factors according to local guidelines. Transfusion support should be administered as clinically indicated. Erythropoietic agents may be used at the discretion of the treating physician according to local guidelines.

### 8.2 Patient Monitoring

#### Blood pressure

Patients should have blood pressure determined weekly for the first cycle of therapy and then at least every two weeks thereafter (see Appendix VII). More frequent blood pressure assessment will be required should hypertension be documented: BP should be repeated daily if BP rises to >150/100 if previously normal or if there is a recurrent persistent (>24 h) increase of >20 mmHg. Management is outlined in section 7.3. Blood pressure data should be recorded as appropriate on the CRFs.

### Cardiac monitoring

Patients with prior anthracycline exposure, previous central thoracic radiation that included heart in radiation port, or a history of NYHA Class II cardiac function should be routinely monitored for changes in LVEF (see section 9.0). Patients should be carefully monitored for clinical signs and symptoms of cardiac failure while receiving sunitinib. Cardiac monitoring of patients without cardiac risk factors should be done at the investigator's discretion.

### Tumour lysis

Patients with bulky solid tumors should be monitored closely for pneumothorax, intestinal fistulae, and intestinal perforation in the event of rapid tumor destruction. This may be seen early in treatment. Tumour-related hemorrhage can be seen in conjunction with tumour degeneration and can be a possible life-threatening event.

### Abdominal tumour degeneration

Serious complications of degeneration or shrinkage of abdominal tumours attached to the bowel wall, including GI perforation, have occurred in patients taking sunitinib. This may happen early in treatment. Tumour related hemorrhage can occur in conjunction with tumour degeneration and can be a possible life-threatening event.

### Hypothyroidism

Patients taking sunitinib can experience a decrease in thyroid function. Patients should be followed closely for the signs of symptoms of hypothyroidism and thyroid hormone replacement should be initiated as appropriate.

### Adrenal gland insufficiency

Although adrenal gland insufficiency is rarely seen with sunitinib treatment, patients should be clinically followed for the signs and symptoms of this complication, especially (1) patients with comorbidities associated with adrenal dysfunction, (2) patients with pre-existing adrenal insufficiency (primary or secondary), and (3) patients with concomitant stress (e.g., fever, infection, bleeding, serious accident, surgery) that may precipitate overt adrenal insufficiency in the presence of subclinical sunitinib-induced adrenal toxicity. If clinically indicated, objective testing for adrenal gland function should be conducted.

#### Skin discoloration

Patients should be alerted to the possibility that sunitinib capsules can cause a yellow discoloration of the skin on direct contact. If this happens, the patient should wash immediately with soap and water.

### Patient Drug Administration

Patients will be provided with a diary for recording the date and exact time that each dose of sunitinib is taken. Patients will be asked to return the diary to the study nurse at each physician's visit, at the end of each cycle.

#### Liver Function

Hepatic impairment and/or failure, have been reported with the use of sunitinib. Patient's liver function tests will be assessed as nonclinically significant before entry into trial, and will be monitored throughout.

### **8.3 Dose Adjustments**

Doses will be reduced for hematologic and other adverse events. Dose adjustments are to be made according to the system showing the greatest degree of toxicity. Adverse events will be graded using the NCI Common Terminology Criteria for Adverse Events Version 3.0 (CTCAE) (see Appendix IV).

#### Sunitinib dose levels\*

Dose Level	Daily Dose
-3	12.5 mg
-2	25 mg
-1	37.5 mg
0	50 mg

\* dispensed using 12.5mg, 25mg and 50mg capsules as applicable

The major toxic effects of sunitinib which may limit dose are: neutropenia, thrombocytopenia, fatigue, hand-foot syndrome, hypertension, and changes in liver enzymes. The guidelines that follow outline dose adjustments for several of these toxic effects. If a patient experiences several adverse events and there are conflicting recommendations, please use the recommended dose adjustment that reduces the dose to the lowest level.

For all dose modifications, please note:

- Cycle length of 6 weeks should be maintained even if doses are missed during the 4 weeks of planned treatment (i.e. treatment interruptions should not re-set the cycle timing such that the next cycle starts earlier and missed doses should not be 'made up' in the observation period during weeks 5 and 6). However, the cycle length may be increased in the event that a new cycle of treatment is delayed.
- Supportive care recommendations for sunitinib-related effects can be found in section 8.1.3.
- Patients requiring more than three dose reductions will be removed from protocol therapy.
- Patients who do not recover from toxic effects as required within 3 weeks will be removed from protocol therapy.
- No dose escalations are permitted after reductions for confirmed toxicity (except for the circumstance as described for QTc prolongation in section 8.3).

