### 8.3.1 Non-Hematologic Adverse Events Related to Sunitinib

### Hypertension Management

Specific guidelines for management of this adverse event are provided in the table below. In addition, guidance on the collection and recording of BP information is provided in Appendix VII.

BP measurements – systolic/diastolic Patients not receiving maxima	Treatment/Dose Modification  I antihypertensive therapy:
140-149 mmHg (systolic) OR 90-99 mmHg (diastolic)	
 
Add new or additional antihypertensive meds or increase dose of existing meds
 
Maintain dose of sunitinib
 

150-179 mmHg (systolic) OR	Add new or additional antihypertensive meds or increase dose of existing meds

100-104 mmHg (diastolic)	
 
Hold sunitinib until BP falls to <140/90
 
Decrease sunitinib by 1 dose level if 2 new antihypertensive drugs added to control BP
 
	
≥ 180 mmHg (systolic)  OR  ≥ 105 mmHg (diastolic)	
 
Hold sunitinib until BP controlled
 
Add new or additional antihypertensive meds or increase dose of existing meds
 
Monitor patient closely for hypotension (if on antihypertensive meds) until sunitinib is restarted.
 
Resume sunitinib at the next lower dose level when BP falls to <140/90
 
	
Hypertensive Crisis	

Discontinue sunitinib; Take off study

Hospitalize patient for management

	
modification of antihypertensiv	tihypertensive therapy (four antihypertensives for 2 weeks without dose ve medications): diuretics, beta blocker or central sympathetic blocker, sodilator or calcium channel blocker (CCB)	
> 160 mmHg (systolic) OR > 105 mmHg (diastolic)	
 
Hold sunitinib
 
Maintain antihypertensive meds and monitor patient closely for hypotension until sunitinib is restarted.
 
Resume treatment at one lower dose level when BP falls to <140/90
 
	
Hypertensive Crisis	

Discontinue sunitinib; Take off study

Hospitalize patient for management

	
* Maximal antihypertensive weeks.	therapy is defined as four antihypertensive medications given for 2	

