### 8.3.4 Other Non-Hematologic Adverse Events

Event	AE Grade	Dose modification
	or	
	Observation	
Fever, chills, flu-like	Grades 1-4	Maintain dose
symptoms		
	Grades 1 and 2	Maintain dose
Fatigue (lethargy,	Grade 3 *	Hold sunitinib until $\leq$ grade 2, then reduce 1 dose
		level and resume treatment
malaise, asthenia)	Grade 4	Hold sunitinib until $\leq$ grade 2, then reduce 1 dose
		level and resume treatment
	>450 but	Review patient's concomitant medications for
	< 550 msec	QT interval-prolonging agents. Correct any
		electrolyte abnormalities.
		Continue sunitinib at current dose level.

\* If neutrophil and/or platelet counts have not recovered to baseline or better within 3 weeks of dose interruption, the patient is withdrawn from the study \* Recurrent grade 3 events require dose reduction.

QTc Prolongation	≥ 550 msec	Stop sunitinib and any other QT-interval prolonging agents immediately. Correct any electrolyte abnormalities, then  1. If there is a plausible explanation for AE other than sunitinib treatment, resume sunitinib at current dose level.  2. If sunitinib may have contributed to the AE:  Reduce 2 dose levels and restart sunitinib.  If QTc remains <500 msec after 14 days at reduced dose, increase one dose level and continue sunitinib.  If QTc remains <500 msec after 14 days, original
		dose of sunitinib may be resumed.
	Grades 1 and 2	Maintain dose
	Grade 3 *	Hold sunitinib until $\leq$ grade 1, then resume
Hand-foot syndrome		treatment at same dose or reduce 1 dose level
	Grade 4	Hold sunitinib until $\leq$ grade 1, then reduce 1 dose
		level or discontinue treatment
	Grades 1-2	Maintain dose *
AST and/or ALT	Grades 3-4	Sunitinib held until ≤grade 2,then resume at dose
elevation		level-1. If grade 3-4 recurs a 2 nd time, discontinue
(SGOT, SGPT)		sunitinib. Also discontinued if there is no resolution
		to < grade 2 on first episode.
Posterior Reversible	Any occurrence	Cease sunitinib and await recovery with
Encephalopathy Syndrome		symptomatic management. Discontinue treatment.
CPK elevation	Grade 2	Hold sunitinib until ≤ grade 2, then reduce 1 dose level and resume treatment

\* Recurrent grade 3 events require dose reduction.

- Patients requiring a delay of > 4 weeks or > 3 dose reductions should go off protocol therapy but may remain at the principal investigators discretion

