- 24-48 hrs are suggested as elapse time between decision steps suggested in the algorithm unless persistent severe hypertension occurred.
- Hypertension should be graded according to NCI CTCAE Version 3.0 and recorded on CRFs.
- While patients are receiving treatment with sunitinib, the early initiation of antihypertensive treatment for grade 1 or 2 hypertension to minimize more severe or persistent hypertension is not considered a grade 3 adverse event.
- Decisions to hold or decrease the sunitinib dose during treatment must be based on BP readings taken in the clinic by a medical professional.

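### Section 8.3 gives inconsistent rules on removal, the lowest dose level, haematological recovery, and the CPK and AST/ALT holds, and the stopping criteria depend on it

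*Combined protocol and SAP*

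**What the plan says.** - **Where it counts.** The trial summary (duration of treatment) and section 12.1 both list unacceptable toxicity, as section 8 defines it, as a reason to stop protocol treatment.
- **General rules, section 8.3.** The list under the dose-level table opens with "For all dose modifications, please note". It includes "Patients who do not recover from toxic effects as required within 3 weeks will be removed from protocol therapy" and "Patients requiring more than three dose reductions will be removed from protocol therapy". The table runs from 50 mg (level 0) to 12.5 mg (level -3).
- **Tie-break, section 8.3.** If a patient has several adverse events with conflicting recommendations: "please use the recommended dose adjustment that reduces the dose to the lowest level".
- **Note under the section 8.3.4 table.** "Patients requiring a delay of > 4 weeks or > 3 dose reductions should go off protocol therapy but may remain at the principal". The rest of that sentence leaves the choice to the person in that role. Four bullets follow, from "24-48 hrs are suggested as elapse time between decision steps suggested in the algorithm unless persistent severe hypertension occurred" to "Decisions to hold or decrease the sunitinib dose during treatment must be based on BP readings taken in the clinic by a medical professional".
- **Section 8.3.3 (haematology).** Grade 3 and 4 neutropenia and thrombocytopenia are held to grade 2 or below and then resumed. The table's footnote withdraws patients whose counts are not at baseline or better within 3 weeks of interruption.
- **Section 8.3.4, CPK row.** The trigger is printed as grade 2. The drug is held to grade 2 or below, then reduced one level.
- **Section 8.3.4, AST/ALT row.** Grades 3-4 are held to grade 2 or below. Treatment stops if a first episode does not resolve to below grade 2, or if grade 3-4 recurs.
- **Section 8.3.5.** For events not covered earlier, 25 mg daily is called the lowest reduced level. Patients whose event does not settle to grade 2 or below at that level are in general removed.

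**The concern.** Section 8.3 is more than supportive guidance, because the protocol uses it to define a discontinuation criterion that three centres will apply. If its passages disagree, the same patient could be taken off treatment under one and kept on, or reduced further, under another. That bears on patient safety and on whether removal from treatment is consistent. The protocol would need to say which passage prevails, and the only precedence rule in section 8.3 is the tie-break.

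**Working it through.** The plan states no figure to reproduce. The check sets the passages side by side, with a little counting.

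**1. Removal**
- *Reductions.* Both passages use more than three, so the counts agree. The general list makes removal mandatory; the 8.3.4 note makes it the default but allows the patient to remain. A patient needing a fourth reduction gets two different answers.
- *Time.* The general list uses 3 weeks: 3 × 7 = 21 days. The note uses more than 4 weeks: 4 × 7 = 28 days. The limits differ by 28 − 21 = 7 days. This assumes both clocks start at the dose interruption, which neither passage states: one refers to recovery from toxic effects, the other to a delay. Beyond both limits, removal is mandatory under one and discretionary under the other.
- *Scope of the note.* All four bullets that follow it refer to hypertension or blood-pressure readings (4 of 4), so it may be a hypertension note. The general list covers all dose modifications, and the hypertension table has holds with no time limit ("Hold sunitinib until BP controlled"). Even on the narrow reading, a hypertension hold falls under both rules.
- *Events outside the time question.* Several events have their own stopping rule: neutrophil and platelet counts (3 weeks), LVEF (2 weeks), posterior reversible encephalopathy syndrome, confirmed heart failure, myocardial infarction and hypertensive crisis. Paroxysmal hypertension (section 8.3.2) has its own exit if control fails, but no time limit.

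**2. Lowest dose**
- Dose-level table: 50 → 37.5 → 25 → 12.5 mg, three reductions. This fits the limit of more than three.
- Section 8.3.5: 50 → 37.5 → 25 mg, two reductions.
- Difference: 3 − 2 = 1 level. At 25 mg, section 8.3.5 points to removal while the table leaves one further step.

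**3. Haematology**
- Resume condition: grade 2 or below. Withdrawal condition: not at baseline or better within 3 weeks.
- Take a patient whose baseline count was better than grade 2 and whose count stands at grade 2 at 3 weeks. Both conditions are met.

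**4. Single rows of the 8.3.4 table**
- *CPK.* Trigger grade 2; release at grade 2 or below. Since 2 ≤ 2, the hold is released as soon as it starts. As printed, grades 3 and 4 have no action. Section 8.3.5 might be meant to cover them, but its heading limits it to events not addressed above, and CPK has its own row.
- *AST/ALT.* An event that settles at exactly grade 2 meets the resume condition (grade 2 or below) and also fails the requirement to resolve to below grade 2.

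**5. Does the tie-break settle any of this?** No. It applies when one patient has several adverse events, and it selects a dose. It does not address removal, discretion, the lowest available level or a threshold within a single event.

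**The case against.** **A reader might infer that none of these rules can be followed together.** The documents do not support that. Removing a patient at 3 weeks breaches nothing in the 8.3.4 note, which does not ask for patients delayed 3 to 4 weeks to be kept on. The 7-day gap is therefore a pair of unequal thresholds, with undefined clocks, rather than an impossibility. The CPK row can also be carried out, as an immediate reduction and resumption. It is a defect inside one row, not a clash between two rules.

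**The layout may exaggerate the problem.** The haematology footnote is printed among the 8.3.4 material, so the scope of the note on delay is uncertain. A comparison sign before the CPK grade may have been lost in text extraction. If it was, the gap at grades 3-4 disappears, but the hold is still empty at grade 2.

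**The more specific note could be read as an exception to the general list.** However, that list states an exception where it allows dose escalation after QTc prolongation, and it states none for removal.

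**Section 8.3.5 is residual guidance, qualified by its own wording.** That limits its reach, but its statement of the lowest level still disagrees with the dose table.

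**A reader might also infer bias in the primary analysis,** since section 10.1.2 generally requires two cycles and a re-evaluation for response evaluability. The documents give no rate of removals under either rule, so that effect can be neither shown nor sized.

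**Conclusion.** The concern holds as a set of inconsistencies inside a stopping criterion:

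- mandatory against discretionary removal, with unequal limits of 3 and more than 4 weeks on undefined clocks;
- a lowest level of 12.5 mg against 25 mg, one dose level apart;
- a haematological resume threshold that can be met together with the withdrawal condition in its own footnote;
- an empty CPK hold at grade 2, and an AST/ALT row whose two thresholds overlap at grade 2.

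Confidence is high on discretion, the lowest level, the empty CPK hold and the haematology footnote. It is moderate on whether the 8.3.4 note reaches beyond hypertension and on the missing CPK grades 3-4. The AST/ALT overlap also turns on a single comparison sign and should be checked against the source file. The 7-day figure assumes a common clock, and the haematology overlap assumes a baseline better than grade 2.

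**What to change.** Issue one clarifying amendment to section 8.3, in which the sponsor's clinical team reconciles:

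1. the general list in section 8.3 with the note and bullets under the 8.3.4 table: the time limit, when the clock starts, whether discretion applies, and whether the note covers hypertension only;
2. the resume threshold in section 8.3.3 with its withdrawal footnote;
3. the dose-level table with the lowest level named in section 8.3.5;
4. the CPK row (trigger, release, and where grades 3-4 are handled) and the AST/ALT row (resume against discontinue).

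One rule should remain in each case. Which limit, dose level or grade that is remains a clinical decision, on which this review takes no position. The cost is the drafting and approval of one amendment, with no added tests, visits or patients.
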